11.3 Investigator Communication with Amgen

11.3.1 Safety reporting to Amgen

The PI and the research team is responsible for compliance with expedited reporting requirements for serious and unexpected and related adverse events (SUSARs), for generation of SAE reports including narratives, and for periodic reporting to Amgen of SAEs as outlined in Table 5 and Table 6 below. Individual safety reports (Table 5) should be accompanied by the Fax Cover Form provided in Appendix 15.1, and sent to Amgen Global Safety, utilizing the fax or email information provided on the cover page. Aggregate safety reporting (Table 6) including listings, tabulations and summary reports should be scanned and accompanied by the Fax Cover Form provided in Appendix 15.5, and sent to Amgen NASCR, utilizing the email information provided on the cover page.

In addition to the requirements outlined in Table 5 and 6, Sponsor/Investigators are required to report direct exposures to talimogene laherparepvec (e.g., needle stick, splash back) of herpetic illness and all suspected herpetic events (refer to Section 11.3.2 ‘Accidental Exposures to Talimogene Laherparepvec and Herpetic Events’).

MDA SAE form will be used for the reporting of these events. Anytime a report (i.e. herpetic, pregnancy, or lactation event) is submitted to Amgen (even though it may not be an SAE by definition), a copy must be provided to the IND Office at the same time.

Table 5. Expedited Reporting Requirements for Interventional Studies

Safety Data	Timeframe for Submission to Amgen
Suspected Unexpected Serious Adverse Reaction (SUSARs)	Individual reports sent to Amgen at time of expedited reporting to IRB and/or FDA.

Serious Adverse Events (SAEs) (related)	Individual reports sent to Amgen at time of expedited reporting to IRB and/or FDA
Pregnancy/Lactation	Individual reports sent within 10 days of Sponsor/Investigator awareness. (Refer to Appendix 15.3 and Appendix 15.4 for Amgen template forms)

Individual reports should be faxed to [name] or scanned and sent via email to [contact]

Table 6. Aggregate Reports

Safety Data	Timeframe for submission to Amgen
Adverse events (all serious and non-serious adverse events, regardless of relatedness)	Line listing and summary tabulation of all adverse events sent annually AND at end of study
US IND Annual Safety Report	Annually
Other Aggregate Analyses (any report containing safety data generated during the course of the study)	At time of ISS sponsor submission to anybody governing research conduct (e.g., RA, IRB, etc.)
Final (End of Study) Report, including:  Unblinding data for blinded studies  Reports of unauthorized use of a marketed product	At time of ISS sponsor submission to anybody governing research conduct (e.g., RA, IRB, etc.) but not later than 1 calendar year after study completion

Aggregate reports should be submitted via email to the Amgen NASCR manager, accompanied by the Fax Cover Form in Appendix 15.5

Please refer to the ICH Guidelines E2A for safety related definitions and terminology:
http://www.ich.org/fileadmin/Public_Web_Site/ICH_Products/Guidelines/Efficacy/E2A/Step4/E2A_Guideline.pdf.

11.3.2 Accidental Exposures to Talimogene Laherparepvec and Herpetic Event Reporting

In order to better assess and understand the potential risks to treated patients and/or third parties following the treatment of clinical trial subjects with talimogene laherparepvec, special reporting procedures apply for accidental exposures to talimogene laherparepvec and for suspected herpetic events. See Table 7 for a summary of reporting requirements. Clinicians should review the Imlygic package insert (available online) for additional information on the safe handling of talimogene laherparepvec.

Accidental Exposure of HCPs to Talimogene Laherparepvec

HCPs involved in your clinical trial who were directly exposed to talimogene laherparepvec (e.g., needle stick, splash back) but who are without signs or symptoms of herpetic illness should be reported to Amgen at [name] ([name]).

Suspected Herpetic Events

Suspected herpetic events must be reported to Amgen within 24 hours of awareness.

Reporting is required for: (1) suspected herpetic events in treated patients; (2) suspected herpetic events in at risk HCPs with direct or indirect exposure and (3) suspected herpetic events in treated patient's close contacts, as outlined in Table 7. An example of the Suspected IMLYGIC™ (Talimogene laherparepvec) or Herpes Virus Associated Adverse Event can be found in Appendix 15.2.

In addition to reporting these events, suspected herpetic lesions should be swabbed and submitted for qPCR testing for the detection of talimogene laherparepvec. Samples should be collected using appropriate technique and a flocked swab from site supplies. This test is likely to be more reliable if performed within the first three days of symptom appearance, however, all lesions should be swabbed, regardless of the timing of presentation. Amgen does not require qPCR or other testing for wild type HSV-1.

➤ **Reporting Process for ISS Treated Patients:**

- Any suspected herpetic lesion should be reported to Amgen at [name] ([name]), evaluated by the Sponsor/Investigator and swabbed for qPCR testing.
- Once an initial report has been made, additional materials will be provided, including reporting forms and supplies needed for shipment of swab samples. Amgen will require patient consent for qPCR testing, which must be obtained prior to swabbing.

➤ **Reporting Process for HCPs and Close Contacts:**

Sponsor/Investigator should advise any HCPs and/or Close Contacts with suspected herpetic lesions to contact their personal physician to facilitate reporting to Amgen. Suspected herpetic lesions can be reported by the Sponsor / Investigator, personal physician or exposed individual to Amgen at [name] ([name]). Once an initial report has been made, additional materials will be provided, including reporting forms and supplies needed for the shipment of swab samples. Amgen will require patient consent for qPCR testing, which must be obtained prior to swabbing.

Table 7. Accidental Exposure & Herpetic Event Reporting Requirement Summary

Exposed Person	Reporter	Timeframe for Reporting to Amgen	Report Mechanism	Timing of Swab Collection	qPCR Testing?	Responsible Party for Lesion Swabbing	qPCR Test Result Distribution*
Treated Patients with suspected herpetic lesions	Sponsor / Investigator	Within 24 hours of Sponsor / Investigator awareness	Contact Amgen at [name] ([name]) to report event	Collect swabs from suspected lesions (ideally within 3 days of appearance of symptoms)	Yes, if consent obtained	Sponsor / Investigator	Sponsor / Investigator and Amgen

HCP directly exposed to product (e.g., needle stick, splash back) without signs or symptoms of herpetic illness	HCP's Personal Physician or impacted person	Within 24 hours of Reporter awareness	Contact Amgen at [name] ([name]) to report event	N/A	N/A	N/A	N/A
HCP directly or indirectly exposed to product with suspected herpetic lesions	HCP's Personal Physician or impacted person	Within 24 hours of Reporter awareness	Contact Amgen at [name] ([name]) to report event	Collect swabs from suspected lesions (ideally within 3 days of appearance of symptoms)	Yes, if consent obtained	HCP or HCP's Personal Physician	HCP's Personal Physician and Amgen
Close Contact (eg caregiver, spouse, child) with suspected herpetic lesions	Sponsor / Investigator, Close Contact's Personal Physician or Close Contact	Within 24 hours of Reporter awareness	Contact Amgen at [name] ([name]) to report event	Collect swabs from suspected lesions (ideally within 3 days of appearance of symptoms)	Yes, if consent obtained	Sponsor / Investigator, Close Contact's Personal Physician	Sponsor / Investigator, Close Contact's Personal Physician and Amgen

*The laboratory conducting the qPCR testing on behalf of Amgen is Viracor.

12.0. Data management

12.1. Data collection and entry

Data collected from the study will be entered in PDMS or CORe.

The Principal Investigator is responsible for assuring that the data entered into the database are complete and accurate and that data entry is performed in a timely manner.

Demographic information, age, sex, race, and date of birth; date of initial breast cancer diagnosis, surgery, local recurrence, and distant metastases if indicated; end date of chemotherapy including targeting agents, radiation therapy, or hormone therapy; menopausal status; clinical and pathologic stage of initial breast cancer; initial tumor histology, nuclear grade, estrogen receptor status, progesterone receptor status, and HER2 status; lymphatic invasion, vascular invasion, and tumor margins; previous chemotherapy regimens including targeting agents, type of surgery, and type of radiation therapy, hormone therapy, etc.; date of treatment, treatment response, levels of overall response, and AEs [≥ 2 non-hematologic and ≥ 3 hematological AEs] will be collected. Grade 2 or higher abnormal lab values will be recorded as AEs; and grade 1 abnormal laboratory values will not be reported as AEs; however, any clinical consequences of the abnormality should be reported as AEs. Concomitant medications will not be entered in the case report form, captured only in the medical record.

12.2. Data confidentiality plan

All laboratory and clinical data gathered in this protocol will be stored in a password-protected database. All patient information will be handled using anonymous identifiers. Linkage to patient identity will be possible only after accessing a password-protected database. Access to the database will be available only to individuals directly involved in the study.

Information gathered for this study will not be reused or disclosed to any other person or entity, or for other research. Once the research has been completed, identifiers will be retained for as long as is required by law and by institutional regulations, and at that point will be destroyed.

13.0. Statistical consideration

13.1. Statistical design

The primary objective of this phase II trial is to assess the efficacy of talimogene laherparepvec as a single agent in locally recurrent IBC and non-IBC patients. The primary endpoint is the rate of overall response.

The overall response rate is defined as the percentage of CR, PR in overall patients. Patients will be evaluated for disease control at the end of cycle 4 (2 months), cycle 8 (4 months) and cycle 10 (5 months). If patients have measurable disease only and achieve CR or PR, they will be considered Response Type I. If patients have non-measurable disease only, and achieved CR, they will be considered as Response Type II. If patients have both measurable and non-measurable disease and achieve CR or PR at the measurable disease sites, and achieved CR at the non-measurable disease site, they will be considered as Response Type III. If patients have mixed responses such as progression of measurable disease and no progression of non-measurable disease at 5 months or vice versa, they will be considered to have uncontrolled disease. The Overall Response rate will be defined as a sum of the 3 response types.

The trial will be conducted using a two-stage design and the overall response rate will be estimated accordingly. It is assumed that the talimogene laherparepvec single agent will have a response rate of 20%. A response rate of 5% or lower will be considered treatment failure and the regimen will be rejected under this circumstance. 13 patients will be enrolled to the first stage. The study accrual will be delayed until all 13 patients are evaluable for response. A summary report will be submitted to the medical monitor in the IND office. If no patients achieve an overall response to the treatment, the trial will be stopped and the regimen will be declared as ineffective. If there are 1 or more patients achieve an overall response, 22 more patients will be enrolled to the study to reach a total of 35 treated patients. By the end of the study, the new regimen will be rejected if less than or equal to 3/35 patients achieve overall response and will not be considered worthy of further investigation otherwise.

We have reviewed the 8 patients treated thus far, and determined that 1 of those 8 patients would not be eligible per the current proposed revised criteria due to extensive ($\geq 5\%$ Total Body Surface) skin lesion and will be replaced. As such, the overall sample size will be increased to 36 by one more patient. The afore mentioned one patient that is still evaluable for toxicity and efficacy in the overall end analysis, but not as a part of the evaluation for the 13 patients treated in the first stage. The above two-stage design statistical analysis plan will not change.

The operating characteristics of the trial are given as follows. When the true response rate is 5% the probability of stopping the trial early is 51% and the probability of claiming the regimen to be promising is 8.4%. On the other hand, if the response rate is 20%, the probability to stop the trial early is 5% and the probability of claiming the regimen to be promising is 90%. The

expected sample sizes are 23.7 and 33.8 when the true overall response rates are 5% and 20%, respectively

We will monitor severe toxicity, grade 3 or greater possibly, probably or definitely treatment related toxicities with CTCAE ver.4.0, by cohorts of 5 patients for the whole patient population (N=36) for the first cycle. A summary report will be submitted to the medical monitor in the IND office. The stopping boundary is calculated based on the beta-binomial distribution. We assume that number of patients who develop severe toxicity follows a binomial distribution with probability p , and p has a prior distribution of beta (0.20, 0.80). We consider that the probability of severe toxicity greater than 20% is excessive to the patients. The stopping boundary is chosen to stop the trial if the data indicate that there is a high probability that excessive toxicity-i.e., probability $(p>0.20|data) \geq 90\%$. The trial will be stopped and the treatment will be considered too toxic if the number of patients with severe toxic effects exceeds $>=3/5, 4/10, 6/15, 7/20, 8/25, 10/30$, and $11/35$ for the first cycle. The operating characteristics are provided, based on 5,000 simulations. For example, if the true toxicity rate is 10%, the probability to stop the trial early due to toxicity is very low, 2% and an average of 34.5 patients will be treated on trial. On the other hand, if the true severe toxicity rate is 30%, the probability of stopping the trial early would be 62% with an average of 21.5 patients treated. When the true severe toxicity rate is 20%, we will have a 21% chance of terminating the trial early with an average of 30.3 patients treated. However if the toxicity rate is as high as 40%, then we will have a 91% chance to stop the trial early and with an average of only 13.5 patients treated.

Secondary objectives includes determining the overall disease control rate, local overall response rate and disease control rate, PFS, and OS in all patients; the local overall response rate and disease control rate, PFS, and OS in patients without distant metastases; and the local overall response rate and disease control rate, PFS, and OS in patients with distant metastases for defining the local efficacy of talimogene laherparepvec injection among breast cancer patients with inoperable local recurrence after surgery. In addition, this includes safety and tolerability of talimogene laherparepvec in these patients. The definition of PFS is time from treatment initiation until disease progression or death and this progression needs to be confirmed after the end of cycle 10. For example, patients who showed progress at 2 months but responded as PR at 5 months, we determine this as PR. In contrast, patients who showed progress at 2 months and was confirmed PD at 5 months, we determine this as PD at 2 months. The definition of OS is time from treatment initiation until any cause of death.

Analysis plan:

By the end of the study, the overall response rate will be estimated with 95% confidence intervals for all evaluable patients and for patients with or without distant metastasis, separately. PFS and OS from registration will also be estimated using Kaplan-Meier method with 95% confidence intervals.

Biomarker endpoints will be measured in tissue and in surrogate blood or plasma before and after the treatment. Correlation between biomarkers from various markers and between tissue and blood/plasma will be assessed by Pearson or Spearman rank correlation coefficients for

continuous biomarkers and by chi-square or Fisher's exact test for discrete covariates. The associations between markers or change in the level of markers and overall response status will first be assessed graphically and then tested using a t-test/analysis of variance or Wilcoxon rank sum test/Kruskal-Wallis test, when appropriate. Repeated measures analysis including mixed effects modeling will be performed to analyze biomarkers change over time. We may also evaluate the association between the changes in the level of marker and the overall response status.

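### The final efficacy rule gives a negative conclusion on both sides of the 3/35 cut-off, so as written no result can be positive

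*Combined protocol and SAP*

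**What the plan says.** Section 13.1 sets out a single-arm two-stage design with overall response rate as the primary endpoint. The unacceptable rate is 5% ("A response rate of 5% or lower will be considered treatment failure and the regimen will be rejected under this circumstance") and the assumed rate is 20%. For the first stage, "13 patients will be enrolled to the first stage", with a futility stop: "If no patients achieve an overall response to the treatment, the trial will be stopped and the regimen will be declared as ineffective". With at least one response, "22 more patients will be enrolled to the study to reach a total of 35 treated patients".

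The rule for the end of the trial is that the regimen will be "rejected if less than or equal to 3/35 patients achieve overall response and will not be considered worthy of further investigation otherwise".

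The same section then gives the operating characteristics. At a true rate of 5%, early stopping has probability 51% and a positive claim 8.4%. For the target rate it reads "if the response rate is 20%, the probability to stop the trial early is 5% and the probability of claiming the regimen to be promising", and puts the latter at 90%. Average enrolment is given as 23.7 patients at the lower rate and 33.8 at the higher. The section also raises total enrolment to 36 to replace one patient, and says that the two-stage plan is unchanged.

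Section 13.2 names the primary endpoint without a threshold. The analysis plan in Section 13.1 promises an estimate with a 95% confidence interval, also without a decision criterion.

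**The concern.** The sentence splits the possible results into two sets: 0 to 3 responses, and everything else. The first set leads to rejection. The second leads to the regimen not being thought worth pursuing. No result leads to a positive conclusion.

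This contradicts the operating characteristics that follow, which attach non-zero probabilities to claiming the regimen promising. Those figures never say which count produces that claim, so a reader has to work it out.

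The trial has no control arm, and its conclusion depends on whether 3 or 4 patients respond. If 4 or more respond, a positive report would contradict the written rule, and the sponsor would be inferring the success criterion after seeing the data. Pre-specification is meant to prevent that.

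**Working it through.** **Inputs (all Section 13.1).** First stage n1 = 13, stop at 0 responses; second stage n2 = 22, total n = 35; true rates p = 5% and 20%. Stated results: positive claim 8.4% and 90%; early stopping 51% and 5%; expected sample size 23.7 and 33.8.

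**Early stopping.** P(stop) = (1 − p)^13.
- p = 5%: 0.95^13 = 0.5133, stated 51%.
- p = 20%: 0.80^13 = 0.0550 (5.498%), stated 5%.

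**Expected sample size.** E[N] = 13 + 22 × (1 − P(stop)).
- p = 5%: 13 + 22 × 0.4867 = 23.71, stated 23.7.
- p = 20%: 13 + 22 × 0.9450 = 33.79, stated 33.8.

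**Positive claim, taking c or more responses in 35 as positive.** The trial must pass the first stage and reach c in total. This equals the chance of c or more in 35, less the chance of none in the first 13 followed by c or more in the next 22:

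P(positive) = P(Bin(35, p) ≥ c) − (1 − p)^13 × P(Bin(22, p) ≥ c).

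For c = 4:
- p = 5%: 0.0958 − 0.5133 × 0.0222 = 0.0958 − 0.0114 = 0.0844.
- p = 20%: 0.9395 − 0.0550 × 0.6680 = 0.9395 − 0.0367 = 0.9028.

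**Which cut-off did the plan use?**

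| Rule at 35 patients | Positive at 5% | Positive at 20% |
|---|---|---|
| Stated in the plan | 8.4% | 90% |
| As literally written | 0% | 0% |
| 3 or more | 20.6% | 93.4% |
| **4 or more** | **8.44%** | **90.28%** |
| 5 or more | 2.7% | 83.1% |

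Of the rules tried, only rejection at 3 or fewer with a positive conclusion at 4 or more matches the stated figures. The literal sentence gives 0% in both columns, because no count is assigned a positive outcome.

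**Side calculation on the denominator.** Section 13.1 keeps the replaced patient evaluable for efficacy in the final analysis but outside the 13 of the first stage. Suppose that patient also counts in the final decision, treated as one more patient outside the first stage, with the threshold kept at 4. Then the second component has 23 patients and the total is 36:
- p = 5%: 0.1037 − 0.5133 × 0.0258 = 0.0904.
- p = 20%: 0.9478 − 0.0550 × 0.7035 = 0.9091.

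The shift is small: 8.4% becomes 9.0%, and 90.3% becomes 90.9%.

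**The case against.** The strongest reply is that this is a slip of the pen with no practical effect. A statistician who reads the rule together with the operating characteristics recovers a single cut-off, as the table shows. The design, sample size, futility stop and reported estimate are all unaffected. The sentence can also be parsed so that both clauses describe the negative outcome and the stray word is otherwise; the rule would then be silent about 4 or more responses instead of negative. On this view the 0% power figure describes no design that anyone intended.

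Much of this stands. It is a drafting error, and the 0% figure is only a consequence of the literal text. But the alternative parse leaves the trial with no written success criterion, so the same correction is needed. That the intent can be recovered by calculation does not replace stating it, since the threshold decides the trial's conclusion and appears nowhere else in words.

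It is also fair to say that a corrected sentence referring to 35 patients leaves open how the replaced patient is handled, now that 36 are to be enrolled. That is a separate and smaller matter, and it does not weaken the case for the correction.

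**Conclusion.** The concern holds and must be fixed. As written, Section 13.1 allows no positive conclusion: the probability of one is 0% at both 5% and 20%, against the plan's own 8.4% and 90%. The plan's figures fit rejection at 3 or fewer and a positive conclusion at 4 or more of 35 (8.44% and 90.28%), so the error is in the wording and not in the design. The calculation assumes independent responses with a common probability, the futility stop at 0/13, and a final decision based on 35 patients. The severity comes from where the error sits, in the only verbal statement of the primary decision rule, and not from any lack of power in the intended design.

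**What to change.** Replace the final sentence of the rule in Section 13.1 with: the regimen will be rejected if 3 or fewer of the 35 patients have an overall response, and will be regarded as worthy of further investigation if 4 or more do.

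In the same edit, state whether the replaced patient counts in this decision or only in the estimate of the response rate. If the decision stays on 35 patients, the published operating characteristics stand unchanged. If it moves to 36 with the threshold at 4, they become about 9.0% and 90.9% under the assumption above and should be restated.

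The cost is a one-sentence protocol correction, plus a clause on the denominator. The correction itself changes no sample size, data collection, trial conduct or error rate. It should be made before the final response data are reviewed.
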